5. STATISTICAL ANALYSIS PLAN

5.1 Statistical Methods – General Aspects

Descriptive statistics (n, frequency, mean, SD, median, range) will be used to characterize the sample in terms of sociodemographic and clinical characteristics and to summarize qualitative outcomes. These characteristics will be summarized for the sample overall, as well as for each site and cluster.

Additional analyses, including various subgroup analyses, to aid in the interpretation of the defined outcome measures may also be conducted and will be described in the Statistical Analysis Plan.

5.1.1 Primary Objective(s): Assess the Process and Potential Benefit of Implementing the AIRQ™, Asthma Checklist, and Educational Resources (PRECISION program) into Clinical Practice during Telehealth and In-Person Visits

Descriptive statistics (n, frequency, mean, SD, and 95% confidence intervals [Cis]) will be used to assess the process and potential benefits when integrating the AIRQ™ on a telehealth and in-person platform. Qualitative interviews will be summarized based on the interviewers' notes and the transcribed interviews. Findings from the touchpoint discussions with sites will be integrated into the qualitative findings. Audio recordings of interviews from clinical site personnel will be referred to as necessary to supplement interviewer notes and transcriptions. The interview results will be summarized in tabular format, with key recommendations, advantages, and disadvantages grouped accordingly. Specifically, barriers, benefits, challenges, ease of implementation, and areas for improvement will be summarized. Lastly, the results from the Post-study Survey will be summarized using descriptive statistics.

5.1.2 Secondary Objective(s): To Assess Patient Visit Satisfaction When the AIRQ™ Is Initiated as Part of a Telehealth or In-Person visit with Their HCP

To assess patient satisfaction with the AIRQ™, descriptive statistics (n, frequency, mean, SD, and 95% CIs) will be used to summarize patients' responses to the ACE Questionnaire.

Subgroup analysis may be conducted to examine responses by site, cluster, platform used, or AIRQ™ score.

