APPENDIX R. PATIENT SOCIODEMOGRAPHICS QUESTIONNAIRE (ENGLISH VERSION)

Please complete all questions, if possible.

1. *What is your age?* _____ years

2. *What is your sex?*
 male female non-binary Other: _____

3. *What is your ethnic background?*
 Hispanic or Latino
 Not Hispanic or Latino

4. *What is your racial background? (Please mark all boxes that apply with an “X.”)*
 White
 Black or African American
 Asian
 Native Hawaiian or other Pacific Islander
 American Indian or Alaska Native
 Other (specify): _____

5. *What is your current living/domestic situation? (Please mark only one box with an “X.”)*
 Living alone
 Living with a spouse, partner, family, or friends
 Other (specify): _____

6. *How would you describe your employment status? (Please mark only one box with an “X.”)*
 Employed, full-time
 Employed, part-time
 Homemaker
 Student
 Unemployed
 Retired
 Disabled
 Other (specify): _____

7. *What is the highest level of education you have completed? (Please mark only one box with an "X.")*

- Less than high school
- Secondary/high school
- Associate degree, technical or trade school
- College/university degree
- Postgraduate school
- Other (specify): _____

8. What is your household's total income from all sources over the past 12 months?

- Less than \$15,000
- \$15,000 to \$29,999
- \$30,000 to \$44,999
- \$45,000 to \$59,999
- \$60,00 to \$74,999
- \$75,000 to \$99,999
- \$100,000 or more
- Prefer not to answer

9. *How old were you when you were diagnosed with asthma? _____*

10. *Do you smoke?*

- Yes, current smoker
- Not currently, but previous smoker
- No, never smoked

Observational Study Protocol
Study Code D2287L00028 [EVA-26645-03]
Version 2.0
Date June 16, 2022

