Sociodemographic Questionnaire. If a follow-up visit (telehealth or in-person) is conducted during the follow-up period, the clinical site will administer the AIRQ® three-month recall version (regardless of timing of follow-up visit). Sites/HCPs will complete a Clinical Case Report Form (CRF) after the initial visit and after the first follow-up visit (if conducted) for each participant. For the initial and first follow-up visit for which patients complete an AIRQ®, HCPs will be required to review the Assess component of the Asthma Checklist and provide their responses on the CRF; while sites are encouraged to use the AIRQ® for any additional follow-up visits during the study and to provide documentation of the AIRQ® scores, additional CRFs will not be completed by the HCPs.

Additionally, Evidera will host a 30-minute conference call with each clinical site for up to four timepoints (touchpoints) to discuss the implementation of PRECISION tools (i.e., frequency of visits to and the number of portable document format (PDF) file views from study website), assess whether sites are meeting their targets for using the telehealth platform, address site questions, and discuss any challenges of implementing the PRECISION program. These meetings will take place at Months 1, 2, 3 (optional), and 6 and will be used to identify any sites that may benefit from participating in a re-training session. The optional Month 3 touchpoint will be based on whether the site has any difficulties with the study.

Study Population: Clinic staff will invite patients age ≥ 13 years with an HCP-confirmed asthma diagnosis who present for a clinic visit (telehealth or in-person) to complete the AIRQ® and participant questionnaires. Each site will aim to recruit approximately 50 to 75 patients with a total sample size ranging from approximately 750 to 1,500 patients. The number of patients recruited from each site may be modified (i.e., able to recruit > 75 patients) to ensure that the target study sample size is obtained.

Inclusion Criteria: Patients must meet all of the following criteria to be eligible for enrollment:

1. ≥ 13 years of age at the time of enrollment
2. Prior diagnosis of HCP-confirmed asthma
3. Able to read, understand, and speak English or Spanish sufficiently to self-complete or be administered the AIRQ™ via telephone, desktop computer, or mobile device (e.g., smartphone, iPad)

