4.3 Other Variables and Covariates

The sample will be characterized by practice cluster: (1) primary care sites (e.g., private practice, FQHC); (2) specialty care sites (pulmonary, asthma/immunology); and (3) novel sites (e.g., pharmacy, nurse practitioners, nurse educators, prescribers and non-prescribers, telehealth component of Allergy and Asthma Network).

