[REDACTED] [REDACTED] [REDACTED] [REDACTED] Descriptive statistics (n, %) will be presented for the ACE Questionnaire (item scores) by practice cluster, visit platform, AIRQ® control score, exacerbation history, education level, language, age, sex, and NEPP step level (Table 7 series). Item responses and scores on the patient-reported outcome measures (AIRQ®, CCI [REDACTED] and ACE) will be compared across groups (practice cluster, visit platform, exacerbation history, education level, language, age, sex and NAEPP step level). For continuous variables, ANOVA will be used to compare mean scores across groups; pairwise comparisons between means will be performed using Scheffe's test adjusting for multiple comparisons for more than two groups. For categorical data, chi-square analyses will be used to compare frequencies by groups. No adjustments will be made for multiple groups.

For the follow-up analysis dataset, a patient disposition table will be developed to descriptively characterize the follow-up analysis set in terms of age group, language, race, and education by practice cluster (Table 8a). The mean time to first follow-up visit will be described (n, %) in Table 8b. For the primary care and specialty clusters, the first follow-up clinical CRF will be completed at the patient's first follow-up visit. For the novel cluster sites where patients are receiving multiple asthma coaching sessions, the follow-up clinical CRF will be completed at their final coaching session.

Descriptive statistics (n, %) will be used to describe patients with a follow-up visit by AIRQ® control level at initial visit (Tables 8c). Descriptive statistics (n, %) will also be used to describe patients with a follow-up visit by exacerbation history, education level, language, age, sex, and NAEPP step level at the initial visit (Tables 8d to 8i). Descriptive statistics (n, %) will be used to describe patients with a follow-up visit by HCP actions at the initial visit overall and by practice cluster (Table 8j to 8m).

Clinical characteristics and visit information from the first follow-up visit will be presented using descriptive statistics (n, mean [SD], median, range) (Tables 9a to 9e). Descriptive statistics (n, mean [SD], median, range) will also be used to present the results (overall and by practice cluster) for the first follow-up AIRQ® scores and control levels (Table 10a). AIRQ® scores from the first follow-up

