Appendix A. Scoring Information

AIRQ®

The AIRQ® includes 10 questions with Yes/No responses. A total AIRQ® score is generated by summing the number of “Yes” responses. The scores for the AIRQ® range from 0–10. Patients with scores of 0 or 1 are considered “well-controlled,” patients with scores of 2–4 are considered “not well-controlled,” and patients with scores of 5–10 are considered “very poorly controlled.”

ACE

There are eight questions on the ACE with Likert scale responses (Strongly Agree, Agree, Disagree, Strongly Disagree), and one open-ended question. There is no total score for the ACE. Scores for each individual item will be described by frequency.

NAEPP Step Coding

Code	Maintenance Therapy	Rescue therapy
Step 1	No daily medication checked	SABA alone with no maintenance therapy ^a
Step 2	Low-dose ICS	SABA with maintenance therapy ^b
	Theophylline Preparations	
	Leukotriene modifier	
	No daily medication checked	ICS+ SABA as rescue therapy alone Fixed dose combination fast-acting LABA/ICS alone as rescue
Step 3	Medium/High-dose ICS	For Steps 3 through 6, step assignment is based on maintenance therapy only.
	Low-dose ICS + LAMA	
	Low-dose ICS+ leukotriene modifier	
	Low-dose ICS + theophylline preparation	
	Low dose ICS + LABA	
Step 4	Medium-dose ICS/LABA	
	Medium dose ICS + LAMA	
	Medium/high dose ICS + theophylline	
	Medium/high dose ICS + leukotriene modifier	
Step 5	High-dose ICS/LABA + LAMA	
	High-dose ICS/LABA	
Step 6 ^c	Any maintenance therapy AND	Chronic oral systemic corticosteroids OR Biologic

^a Possible alternative: “SABA as rescue therapy via nebulizer without other rescue or maintenance therapies” or “Primatene Mist as rescue and no maintenance therapy”

^b Possible Alternative: “SABA as rescue therapy via nebulizer with other rescue maintenance therapies” or “Primatene Mist as rescue with maintenance therapy(s)”

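### Scheffé's test is valid but needlessly conservative for the SAP's pairwise comparisons: at an assumed 5% familywise level, the critical difference for six NAEPP steps is about 17% larger than Tukey-Kramer's

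*SAP*

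**What the plan says.** SAP section 5.1 compares item responses and scores on the patient-reported measures across eight factors: "practice cluster, visit platform, exacerbation history, education level, language, age, sex and NAEPP step level". The SAP then gives its method for means: "For continuous variables, ANOVA will be used to compare mean scores across groups". Where a factor has more than two groups, it adds that "pairwise comparisons between means will be performed using Scheffe"'s test, described there as an adjustment for multiple comparisons. The section names no contrast other than pairs, gives no reason for choosing Scheffé, states no significance level and does not plan confidence intervals for the pairwise differences. Its chi-square comparisons get no multiplicity adjustment. SAP section 6.2 then lists multiple-comparison adjustment as not applicable, which does not fit the Scheffé adjustment in 5.1.

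The number of groups comes from three places:
- **NAEPP step.** The coding table in SAP Appendix A defines Steps 1 to 6. Its note that "For Steps 3 through 6, step assignment is based on maintenance therapy only" confirms six assignable levels.
- **Education.** The Protocol Appendix R item "What is the highest level of education you have completed" has six boxes, one of them for other answers. The SAP does not say whether boxes are merged.
- **Practice cluster.** "The sample will be characterized by practice cluster" (SAP section 4.3), with three clusters listed. SAP Appendix B later puts novel-site results in separate tables.

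**The concern.** A simultaneous procedure should match the set of comparisons it protects. Scheffé's multiplier is large enough to cover all linear contrasts of the group means, for example the average of Steps 1 to 3 against the average of Steps 4 to 6. If only pairs are examined, part of that protection buys nothing. Tukey-Kramer controls the familywise error for all pairs at the same nominal level, allows unequal group sizes, and has a smaller multiplier whenever there are more than two groups.

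What is at stake is power. The larger multiplier raises the difference that two groups must show before they are called different, so a true difference between, say, two NAEPP steps in mean AIRQ score is more likely to be reported as non-significant. The cost grows with the number of groups.

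**Working it through.** The documents give no critical value, power or alpha for these comparisons, and no formal sample size calculation, so there is no stated figure to reproduce.

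**Inputs**
- k = 6 for NAEPP step (SAP Appendix A); k = 6 for education if all boxes in Protocol Appendix R are kept; k = 3 for practice cluster (SAP section 4.3).
- N: the SAP plans recruitment "with a total sample size ranging from approximately 750 to 1,500 patients". N = 900 is used below, and both ends of the range were checked.
- Familywise alpha: assumed 0.05, in line with the "95% confidence intervals" that the protocol's statistical section uses for other summaries. Range checked: 0.01 to 0.10.

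**Multipliers of the standard error for a pairwise difference**
- Scheffé: sqrt((k − 1) × F[0.95; k − 1, N − k])
- Tukey-Kramer: q[0.95; k, N − k] / sqrt(2)

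The standard error is the same under both methods and cancels from their ratio, so the ratio does not depend on SD or group sizes.

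**Results at N = 900**

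| k | Scheffé | Tukey-Kramer | Ratio | Ratio squared | Familywise error of Scheffé over pairs (equal groups) |
|---|---|---|---|---|---|
| 3 | sqrt(2 × 3.006) = 2.452 | 3.320/1.414 = 2.348 | 1.044 | 1.091 | about 3.8% |
| 6 | sqrt(5 × 2.224) = 3.335 | 4.039/1.414 = 2.856 | 1.168 | 1.363 | about 1.1% |

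The squared ratio converts to patients. At k = 6, Scheffé needs about 36% more patients for the same critical difference, equivalent to giving up 1 − 1/1.363 = 27% of them. At k = 3 the equivalent loss is 1 − 1/1.091 = 8%.

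**Sensitivity**
- N: at k = 6 the ratio is 1.168 at both 750 and 1,500 patients.
- Alpha: at k = 6 and N = 750 it is 1.155 for alpha 0.01 and 1.174 for alpha 0.10.
- Comparator: against Bonferroni over 15 pairs, the k = 6 ratio is 1.133.
- Groups: at k = 2 it is exactly 1; at k = 4 and 5 it is 1.088 and 1.129, which would apply to education if boxes were merged.

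**Power illustration for k = 6.** The SD of 2.5 AIRQ points and 150 patients in each step (6 × 150 = 900) are assumptions, not figures from the documents. SE = 2.5 × sqrt(2/150) = 0.289. The critical difference is 3.335 × 0.289 = 0.96 points under Scheffé and 2.856 × 0.289 = 0.82 under Tukey-Kramer. Power is approximately the normal probability Φ(difference/SE − multiplier):

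| True difference | Difference/SE | Scheffé | Tukey-Kramer |
|---|---|---|---|
| 0.5 | 1.73 | 5% | 13% |
| 0.9 | 3.12 | 41% | 60% |
| 1.0 | 3.46 | 55% | 73% |
| 1.5 | 5.20 | 97% | 99% |

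The gap is largest near 0.9 points, roughly midway between the two critical differences, and shrinks on either side.

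**The case against.** The strongest defence is that Scheffé is a legitimate choice. It controls familywise error, allows unequal groups, and agrees with the planned ANOVA: no pair can be significant when the F test is not. Tukey-Kramer lacks that last property. With eight factors and several instruments tested and no adjustment across them, some conservatism may look prudent. All of this stands as a reason for low weight. It does not make Scheffé the better match for a family of pairs, and conservatism is not the SAP's consistent policy, since the chi-square comparisons are left unadjusted.

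The study is also descriptive. That statement, however, concerns the primary objective; section 5.1 does plan these tests, and Appendix B adds further tests between practice clusters.

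A reader might infer more than the documents support:
- *That a declared 5% level goes unused.* No alpha is stated for these tests, so no declared error rate is missed.
- *That published intervals will be too wide.* Section 5.1 plans tests, not intervals, for these pairs. The effect is a larger critical difference.
- *That 17% applies throughout.* Only NAEPP step is firmly six-level. Practice cluster is barely affected. For that factor there is also an opposing issue: patients are grouped within sites and section 5.1 describes no allowance for site. With 50 patients per site and an assumed intraclass correlation of 0.01 to 0.05, the design effect is 1 + 49 × 0.01 = 1.49 to 1 + 49 × 0.05 = 3.45, which would outweigh a 4% excess.
- *That real differences will be missed.* That is a probability, which depends on the true difference and on the assumed SD and group sizes.

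Finally, the exploratory methods are redacted, so a non-pairwise contrast there cannot be ruled out. The visible plan names none.

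**Conclusion.** The point holds as a minor efficiency weakness, not an error. For the pairwise comparisons that section 5.1 describes, Scheffé demands a critical difference about 17% larger than Tukey-Kramer's across the six NAEPP steps. The range is 15% to 17% for alpha from 0.01 to 0.10, and the figure hardly changes over the planned sample size. It carries over to education only if the six boxes are kept separate. For three practice clusters the excess is about 4%, and there is none if the separate novel-site tables leave two. The 17% rests on an assumed 5% familywise level and on Tukey-Kramer as comparator; the power figures also rest on the assumed SD and equal group sizes. Type I error is not inflated, and the primary objective is untouched.

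**What to change.** - In SAP section 5.1, name Tukey-Kramer for pairwise comparisons of means after ANOVA, and state the familywise alpha. Keep Scheffé only if a non-pairwise contrast is actually planned, and then name that contrast.
- Align section 6.2 with 5.1 by saying which comparisons are adjusted and which are not.
- Appendix B, dated 27 September 2023, reports inferential tests as already run. Record the change as a post hoc revision and keep the Scheffé results beside the new ones, because the replacement can only reject the same pairs or more.

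The direct cost is one phrase in the SAP and one software option, with the pairwise tables rerun from the same ANOVA models and no new data. There are two statistical downsides: a pair may be significant when the F test is not, and any non-pairwise contrast examined later loses automatic protection.

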4.1.3.3 ACE Questionnaire

The ACE Questionnaire is a self-administered electronic questionnaire that includes eight questions using a four-point Likert scale (strongly agree, agree, disagree, strongly disagree) and one open-ended question regarding additional comments about their visit or the AIRQ®. Patients who agree will be sent this questionnaire via an e-mailed survey link following their initial visit. Patients are asked to think about how completing the AIRQ® as part of their in-person or telehealth visit may have affected their experience when answering the questions.

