4.2 Outcomes

4.2.1 Primary Outcome

To address the primary objective of assessing the process and potential benefits when integrating the AIRQ® PRECISION program on a telehealth or in-person platform, the following outcomes will be assessed:

- **Post-study Telehealth Survey:** Descriptive statistics (n, frequency, mean, and standard deviation [SD]) will be used to summarize the results from the Post-study Survey.
- **Qualitative Interviews:** Results from the qualitative interviews will be summarized in a tabular format, with key recommendations, advantages, and disadvantages grouped. Specifically, barriers, benefits, challenges, ease of implementation, and areas for improvement will be summarized. Also, the summary will capture if the PRECISION program has been utilized in clinical practice post-implementation, or what would need to be done to support the continued use of the PRECISION program in their clinical practice.
- **Implementation Touchpoint Discussion with Sites:** Key findings from the implementation questions discussed during the clinical site touchpoint meetings (including barriers and subsequent ways in which these barriers were addressed) will be summarized.

Qualitative findings from the interviews and implementation touchpoints will be interpreted in the context of the Knowledge-to-Action Framework (Graham et al. 2006; Singh et al. 2020), which describes a process to translate new knowledge into sustainable evidence-based interventions that can be applied in clinical practice (In-text Figure 1). In this context, the findings will be used in the action cycle to identify challenges, barriers, and benefits to implementing the AIRQ® and PRECISION tools into clinical practice. The knowledge will be evaluated in local contexts (e.g., practice clusters) and will be monitored throughout the implementation and sustainability period.

In-text Figure 1. Knowledge-to-Action Framework**4.2.2 Secondary Outcome(s)**

1. To address the secondary objective of assessing patient telehealth or in-person visit satisfaction when the AIRQ® is initiated as part of a telehealth or in-person visit with their HCP, the following outcomes will be assessed:
 - o ACE Questionnaire Responses: Descriptive statistics (n, frequency, mean, and SD) will be used to summarize by item for all items. In addition,
2. To explore change in AIRQ® scores from initial visit to follow-up visits:
 - o AIRQ® (initial study visit)
 - o Follow-up AIRQ® (follow-up visits)

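### SAP 5.1 sends ordered ACE item responses (and, by inference, AIRQ control level) to a chi-square test that ignores response order; a row-mean-score test would be as valid and more powerful against a shift in responses

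*SAP*

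**What the plan says.** SAP 5.1 sets up between-group tests. "Item responses and scores on the patient-reported outcome measures (AIRQ" and the other instruments) "will be compared across groups (practice cluster, visit platform, exacerbation history, education level, language, age, sex and NAEPP step level"). Two tests are named. Continuous variables get ANOVA with Scheffé pairwise comparisons. For the rest: "For categorical data, chi-square analyses will be used to compare frequencies by groups". No rank, trend, Cochran-Mantel-Haenszel (CMH) or ordinal-regression method appears in the readable text for these comparisons, and SAP Appendix B adds none.

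The ACE has "eight questions using a four-point Likert scale (strongly agree, agree, disagree, strongly disagree") plus one open-ended question (SAP 4.1.3.3). SAP Appendix A gives it no total score and adds: "Scores for each individual item will be described by frequency". SAP 5.1 and 5.1.2 also present ACE items as n and %. SAP 4.2.2 reads differently: "ACE Questionnaire Responses: Descriptive statistics (n, frequency, mean, and SD) will be used to summarize by item for all items". Protocol 4.2.2 likewise lists item means and SDs, and Protocol 5.1.2 adds 95% CIs.

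AIRQ control level has three ordered classes (scores 0–1, 2–4 and 5–10), and NAEPP step coding has six (both in SAP Appendix A).

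**The concern.** A plain chi-square test gives the same p-value however the answer columns are shuffled. It therefore spreads its power over every kind of difference between groups. The question of interest is narrower: whether patients in one group answer more or less favourably than in another. ACE responses are the outcome for the first secondary objective, and the SAP has chosen to test them. With four answer levels and up to six groups, many degrees of freedom go to patterns that nobody is asking about, and a real shift is more likely to be missed than it need be.

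**Working it through.** **Which test applies.** The ACE has no total score, and SAP 5.1, 5.1.2 and Appendix A report its items as frequencies. On that reading the items are categorical and go to chi-square. For control level this is an inference: it is a categorical AIRQ result with no other between-group test named for it.

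**No figure to reproduce.** The documents give no alpha, power or effect size for these tests, and no expected number of ACE respondents. Total enrolment is 750 to 1,500, and ACE data come only from web-survey completers. Everything below assumes two-sided alpha 0.05.

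**Cost in degrees of freedom.** Chi-square has (groups − 1) × (levels − 1) df; the row-mean-score test has (groups − 1). If a difference is a pure shift, both statistics have about the same noncentrality λ. Let λ(df) be the value that gives 80% power; for 1 df it is (1.960 + 0.842)² = 7.849. Chi-square power is then P[χ²(df, λ) > χ²₀.₉₅(df)], with λ set so that the row-mean-score test has 80%. The sample-size ratio is λ(chi-square df) / λ(row-mean-score df).

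| Comparison | Chi-square df | Row-mean df | Chi-square power when row-mean has 80% | N ratio |
|---|---|---|---|---|
| ACE item × platform | 3 | 1 | 64.5% | 10.90/7.849 = 1.39 |
| Control × platform | 2 | 1 | 70.9% | 9.635/7.849 = 1.23 |
| ACE item × 3 clusters | 6 | 2 | 62.5% | 13.62/9.635 = 1.41 |
| Control × 3 clusters | 4 | 2 | 69.8% | 11.94/9.635 = 1.24 |
| ACE item × 6 NAEPP steps | 15 | 5 | 58.9% | 18.81/12.83 = 1.47 |
| Control × 6 NAEPP steps | 10 | 5 | 67.6% | 16.24/12.83 = 1.27 |

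**Simulation, ACE item.** Assumptions: 500 respondents, answers 45/42/9/4%, proportional odds. Ranges come from repeated runs; for NAEPP step they also reflect different assumed step shares.

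| Scenario | Chi-square | Row-mean-score |
|---|---|---|
| Platform, 125 v 375, odds ratio 1.5 | about 40% | about 53% |
| Three clusters, odds ratios 1/1.3/1.6 | 32–35% | 49–51% |
| Six steps, end-to-end odds ratio 2 | 26–32% | 42–51% |

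**Other sample sizes.** Here the effect was set so that a 1-df linear trend test has about 80% power. Assumed step shares are 10/15/15/20/20/20% and the platform split is 75/25.
- ACE × six steps (answers 45/43/9/3%): chi-square 40% v row-mean-score 59% at N = 300; 41% v 61% at N = 750.
- Control level × six steps (30/35/35%): 42% v 55% at N = 750; 41% v 55% at N = 1,500.
- ACE × platform: 65% v 84% at N = 300; 67% v 83% at N = 750.
- Control level × platform: 69% v 79% at N = 750.

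**Validity.** With no true difference, rejection rates in these last runs were 4.1–5.5% for chi-square, row-mean-score and trend tests. In the six-step ACE scenario with 500 respondents they were 4.8%, 4.7% and 5.4%. The issue is power, not type I error.

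**Non-monotone patterns.** For control level across six steps at N = 750, log-odds shifts of 0.35 × (1, 0, −1, −1, 0, 1) gave 83% power for chi-square, 92% for row-mean-score and 12% for the trend test. A second U-shaped example gave 42%, 66% and 6%.

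**The case against.** - **ACE items may go to ANOVA.** SAP 4.2.2 lists item means and SDs, and SAP 5.1 sends mean scores to ANOVA. ANOVA on items scored 1–4 had 50% power for platform (row-mean-score 54%, chi-square 41%) and 48% for clusters (51% and 35%), so most of the loss would vanish. This stands as an ambiguity. The frequency wording in SAP 5.1, 5.1.2 and Appendix A points the other way, and the SAP needs to say which applies.
- **Control level is partly covered.** The 0–10 AIRQ total, from which control level is cut, goes to ANOVA and keeps its order. This stands, and makes the control-level part the lesser one.
- **Sparse cells.** A reader might infer that few disagree answers invalidate chi-square. The null rejection rates near 5% do not support that.
- **Direction.** A reader might infer that a significant chi-square cannot be read as better or worse. The p-value alone cannot, but the planned n and % tables show direction.
- **A trend test as replacement.** For six steps with a steady gradient, a 1-df trend test reached 77% where chi-square had 32%. It is tempting to prescribe it alone. The documents state no monotone hypothesis, and the U-shaped examples show it can do far worse than chi-square.
- **AIRQ control as a grouping factor.** It is in the descriptive list for the ACE tables but not in the list of tested factors, so no change of test is needed for it.
- **Scope.** The primary objective is descriptive and there is no formal sample size. SAP Appendix B drops the language analyses, moves novel-site results to separate tables and drops several of them for small numbers, so the three-cluster scenario may not match what was run. All of this limits the impact.

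**Conclusion.** The point holds as a matter of efficiency. On the most natural reading, the SAP tests four-level ordered ACE items, and by inference three-level control classes, with a valid test that ignores response order. Against a shift in responses, an ACE comparison by chi-square needs about 1.4 to 1.5 times the sample of a row-mean-score test, and a control-level comparison about 1.2 to 1.3 times. In the assumed 500-respondent ACE scenarios, power falls by roughly 13 to 19 percentage points. The df penalty is general, but the power figures rest on assumed respondent numbers, answer distributions, group shares, odds ratios and proportional odds. Real differences are more likely to be missed; it does not follow that they will be. Only secondary and other comparisons are affected.

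**What to change.** In SAP 5.1:
- Test ACE items and AIRQ control level with the CMH row-mean-score test using rank scores (Kruskal-Wallis), for all tested grouping factors.
- Leave out the Not Applicable answers that the form in Protocol Appendix L offers on ACE items 4–6, and report their number.
- Add the 1-df trend test as a supplement for the ordered tested factors (NAEPP step, education, age). State how the Other education category is handled.
- Report a common odds ratio with 95% CI.
- Keep chi-square for the yes/no AIRQ items and for nominal variables.
- Align SAP 4.2.2 with this choice, so that it is clear whether ACE item means are used at all.

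The cost is SAP wording and a test option in existing code; no new data are needed. The small downside is that differences in the spread of answers without a shift are less well detected, but the frequency tables still show them. SAP Appendix B is written in the past tense; if the analyses are complete, report these tests as a labelled sensitivity analysis.
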